#### UNCONTROLLED WHEN PRINTED

Port	Following implantation, the integration rim, including the access ports,
indicators	are expected to be covered by conjunctiva. A set of indicators on the
	optic's edge that are visible under a microscope assist the surgeon in
	locating the access ports post implantation.
	The port indicators, which are essentially tiny "bumps" on the surface
	of the PMMA, are placed on the edge of the central optical zone; one
	opposite each access port, and two opposite the main access port.
Integration	The integration holes on the rim of the lens are filled with the skirt
holes	material. Connective tissue is expected to grow through these holes,
	practically "biostitching" the PMMA lens onto the sclera. This
	mechanism further ensures device attachment, mitigating risks of
	detachment in case the skirt fibers weaken or detaches from the lens.

# Integrating skirt

The CorNeat KPro integrating skirt is made from a flexible, durable and non-degradable porous material that stimulates cellular proliferation. The skirt is 250 microns thick and easily placed under the conjunctiva. The skirt extends 6mm from the edge of the lens transparent zone (1cm in diameter) and ends approximately 1mm from the closest insertion of the extraocular muscles (spiral of tillaux).

The skirt dimensions are designed to fit most eyes. Nonetheless, it can be easily cut and adjusted by the surgeon to fit any eye.

# 4.2.4 Indications for Use

The ultimate intent of CorNeat Vision is to approve the CorNeat KPro as an **alternative to SOC - penetrating, or full thickness, corneal transplantation (Penetrating Keratoplasty, PKP)** where patient tissue is replaced with donor tissue. Section 4.2.6 below outlines PKP indications. Given the commercial and clinical risks involved, CorNeat Vision plans to undertake a stepwise approach, initially seeking approval of the CorNeat KPro device and implantation kit for patients who are poor candidates for PKP. For these indications there is a regulatory precedent as documented in FDA guidance on 510(k) submissions for KPros dated March 3, 1999. These initial indications for use are similar to those that apply to commercially available synthetic corneal implants, such as the Boston KPro. Section 4.2.54.2.5 outlines current indications of use for KPros. The initial intended use for the CorNeat KPro is defined below and is consistent with the FDA's definition of Class II special controls.

Per the FDA guidance for the initial first step, The CorNeat KPro device will be defined as a "keratoprosthesis device implanted permanently to provide a transparent optical pathway through an opacified cornea in an eye that is not a reasonable candidate for a corneal transplant."

As a second step, and once the device safety is validated in a limited clinical study (per the applicable FDA guidance), CorNeat Vision plans to take the necessary steps and initiate additional clinical trial/s and expand the indications for use to also cover those of PKP. In the treatment of corneal opacities, keratoplasty is the SOC. For some medical indications causing corneal opacities, failure rates of keratoplasty are unacceptable. Patients not suitable

**CONFIDENTIAL** - THIS DOCUMENT CONTAINS CONFIDENTIAL AND PROPRIETARY INFORMATION. THIS DOCUMENT MAY NOT BE REPRODUCED, USED, OR DISCLOSED TO ANY THIRD PARTY WITHOUT PRIOR WRITTEN CONSENT.

for keratoplasty may attempt keratoprosthesis implantation as a last resort. The following sections outline the major indications for both patient groups.

### 4.2.5 KPro Indications

- Following corneal transplantation failure
- Vascularized cornea (at least two quadrants)
- Disciform corneal scar due to herpetic keratitis
- Stevens-Johnson syndrome (SJS)
- Ocular cicatricial pemphigoid (OCP)
- Autoimmune diseases
- Ocular burns (acid and alkali) with stem cell deficiency
- Other conditions with poor prognosis with traditional PKP

#### 4.2.6 PKP Indications

- Keratoconus and ectasias
- Corneal degenerations
- Corneal dystrophies including Fuchs endothelial dystrophy
- Ulcerative keratitis infectious and non-infectious
- Post infectious keratitis
- Congenital opacities
- Chemical injuries without stem cell deficiency
- Mechanical trauma
- Refractive indications
- Regraft related to allograft rejection
- Regraft unrelated to allograft rejection

#### 4.2.7 Implantation Procedure

The CorNeat KPro implantation procedure is relatively short (30-45 minutes) and simple when compared to keratoplasty and other KPros. Unlike current practices requiring delicate suturing of transparent donor corneal tissue to the patient's native cornea – a process which is performed by very skilled and well-trained ophthalmic surgeons – the CorNeat KPro snaps into the patient's trephined cornea and is sutured to the eye wall using 3 non-degradable sutures. The provided Marker and Snapper tools enable precise fitting of the device, yielding a well-developed implantation process, which can be taught in a few hours. The process itself minimizes the time the eye is trephined and open (also known as "open sky") to less than one minute, significantly reducing the risk of infection, expulsive hemorrhage, and other complications.

**Optional**: In cases where the recipient cornea is suspected of being overly stiff, it is recommended to remove two of the posterior rim flanges to facilitate extension of the trephined corneal stump around the posterior turret and insertion into the undercut. If required, place the

CorNeat KPro - Clinical Investigational Protocol

KPro on a sterile gauze pad under a microscope, and locate the 2 o'clock and 4 o'clock flanges using the port indicators (note that when viewing the implant from the posterior aspect, the clock positions are anti-clockwise- see Figure 5). Gently hold down the implant using a soft swab and using a needle holder or other tool, grasp the 2 o'clock flange. Bend the flange inward from the posterior turret to completely break it off. The flange stump should be nearly flush with the posterior rim or slightly recessed (see Figure 6). Repeat the procedure with the 4 o'clock flange. Examine the lens for any cracks, residual sharp edges, particles or lens damage before proceeding.

Figure 7 - Note the clock positions of the posterior rim flanges relative to the port indicators.

*Figure 8 - Illustration of flange removal from the posterior turret* 

	2. Conveat KPro implantation procedure steps						
Step #	Description	Illustration					
1.	Perform peritomy 360°, creating a deep pocket.						
2.	Completely debride the corneal epithelium	Egithelium removal					
3.	Mark the center of the cornea with a surgical marker. This ensures that subsequent critical procedure steps are aligned.						
4.	Cornea marking. Using the dedicated Marker tool, the cornea surface is marked. The marked pattern includes 3 pairs of suturing marks, 4 potential paracenteses lines, and a trephination edge mark. The marker head is transparent and includes a rounded hole centered on the cornea by aligning it with the central mark. The marker and implant are not symmetrical, and care should be taken to align the superior suturing marks with the corneal 12 o'clock position.						

Table 2: CorNeat KPro implantation procedure steps

#### UNCONTROLLED WHEN PRINTED

CorNeat KPro - Clinical Investigational Protocol

Step #	Description	Illustration
5.	Paracenteses + OVD. Two clear corneal incisions are created where indicated by the paracentesis line, and the eye is filled with viscoelastic (OVD).	
6.	Preplace 3 pairs of non-degradable sutures, passing first through dedicated holes on the rim of the KPro's optics, and then through the cornea – entering at the suture hole marks, passing radially through the sclera. Double armed sutures are recommended. Be sure to align the sutures so that they do not cross or become entangled. Inspect the rim of the KPro implant to ensure its integrity before implantation.	
7.	Once all preparatory steps are completed, trephine the central cornea . Align the trephine crosshairs with the central corneal mark to achieve centration.	Trephination
8.	Fasten the implant to the device is fastened to the eye wall by tightening the 3 sutures, and then tying them between the device skirt and the sclera.	KPro Positioning KPro Positioning

CorNeat KPro - Clinical Investigational Protocol

Step #	Description	Illustration
9.	Using the Snapper, Insert the trephined corneal edge, which is stained for better visualization, into the KPro's posterior (corneal) undercut.	KPro Fitting Using the Snapper
10.	Exchange the viscoelastic (OVD) with balanced salt solution (BSS).	
11.	Reposition the conjunctiva and suture into place using degradable sutures. The conjunctiva should completely cover the skirt.,Following conjunctival suturing, apply tissue adhesive to ensure tissue approximation during the initial healing period.	

In every implantation procedure, an extra CorNeat KPro unit and a corneal graft will be ready in the operating room and will be used in case of an unexpected intraoperative complication preventing implantation of the dispensed CorNeat KPro unit.

A full animated video of the CorNeat KPro implantation procedure can be found on the CorNeat Vision website here: https://www.CorNeat.com/kpro-animation

Figure 9: CorNeat KPro implantation animation (CTRL+Click to access)

# 4.2.8 Principles of Operation

The patented design of the CorNeat KPro and the unique implantation procedure include five mechanisms which ensure short- and long-term integration, retention, and water tightness (see Table 3 below). While short-term water tightness is achieved by mechanical means, long-term integration, retention, and water tightness are based on the device's unique skirt, which is implanted subconjunctivally. This porous skirt, made from non-degradable and non-woven fibers, extends near the extraocular muscles' insertions, serving as a scaffold for migration of

fibroblasts from Tenon's capsule (thin membrane enveloping the eyeball from the extraocular muscle insertions to the limbus) and subconjunctival fibrous tissue into the skirt of the CorNeat KPro. This unique integration concept, which has been validated in multiple animal studies, permanently attaches the device to the eye and seals it. Within several weeks, fibroblasts colonize the skirt and sprout collagen within it (Figures 8-11).

Table 3: Short and long-term retention features

Time of action Mechanism	Short term retention Water tightness Ease of implantation	Long term retention Globe integrity			
Posterior undercut	$\checkmark$				
Posterior flanges	$\checkmark$				
3 non-degradable safety sutures	$\checkmark$	$\checkmark$			
Bio-integrative porous, polymeric skirt		$\checkmark$			
5 Bio-integration grooves		$\checkmark$			

Figure 10: CorNeat KPro skirt laid between the sclera and the conjunctiva NZW rabbit histopathology slide showing no inflammation/capsule around the skirt 1- month post implantation

#### UNCONTROLLED WHEN PRINTED

Figure 11: NZW histopathology slide stained with Mason Trichome showing fibroblasts (pink) and collagen (blue) within the device's skirt as it is laid between the sclera and the conjunctiva

Figure 12: NZW histopathology slide stained with Mason Trichome 6 months post operation. The device's skirt is fully colonized with fibroblasts (pink) and collagen (purple)

Figure 13: CorNeat KPro integration concept proven in an NZW rabbit (6 months post operation)

The mechanisms that hold the device's lens in place and seal the eye in the short term enable the skirt to integrate. These include the device posterior (corneal) undercut, which hosts the recipient corneal stump – a set of flanges on the posterior side mitigating the risk of the stump slipping out of the undercut – and 3 sets of non-degradable sutures securing the lens onto the sclera. This mechanism, which ensures water tightness, was tested in cadaver eyes and validated to withstand an Intra Ocular Pressure (IOP) greater than 3X the upper limit of normal IOP, with no leaks. The mechanism is based on the fact that the central cylinder, which traverses the native cornea, is larger in diameter than the trephination. The native corneal stump, which is pushed against the PMMA cylinder, creates a seal that prevents aqueous humor from leaking out. The short-term mechanisms that secure the device into place reduces the skirt's movements and stabilizes it in a way that enables its biological integration (see Figures 12-15).

Figure 14: CorNeat KPro illustration showing how short-term water tightness is achieved. The lens' cross section shows how the native corneal stump fits into the device's corneal undercut as well as 2 of the 3 non-degradable sutures securing the device onto the sclera.

Figure 15: CorNeat Lens water tightness test performed on cadaver eye Intraocular pressure raised to 3X the normal pressure using BSS infusion

In order to further ensure long term retention, the KPro's PMMA lens is surrounded by a set of curved integration holes. These holes are filled with skirt material, which stimulates cellular growth and colonization. It is expected that connecting tissue will grow through the holes, thus "bio-stitching" the PMMA to the eye wall. This function was validated in animal implantations.

CorNeat KPro - Clinical Investigational Protocol

Figure 16 : CorNeat KPro illustration - blue area represents optics integration rim sandwiched by the skirt material

Figure 17: A cross section of the integration rim showing an integration hole filled with the skirt material

# 4.2.9 Regulatory History

There is no regulatory history for the CorNeat KPro device and respective implantation kit. For the initial indications for use, which are detailed in section 4.2.5, FDA submission will be based on guidance on 510(k) submissions for KPros dated March 3, 1999. Product will be classified as class II special controls.

CorNeat Vision does not have regulatory history as all its products are currently in development phases. Company products are developed and validated in compliance with relevant standards and QMS system is implemented and audited as required.

# 5 Study Objectives And Endpoints

# 5.1 Objective

The objective of this clinical trial is to prove the safety and efficacy of the CorNeat KPro device intra and post-operatively.

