# 3 Study Synopsis

# Study Name:

Prospective, open label, single arm, First in Human clinical study to assess Safety and efficacy of the CorNeat Keratoprosthesis for the treatment of corneal blindness

**Objectives**: The objective of this clinical study is to prove the safety of the CorNeat Keratoprosthesis (KPro).

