# Effectiveness Endpoints:

Primary Endpoint: Retention of implant Secondary Endpoint: Improved visual acuity

**Intended uses**: The CorNeat KPro's intended use is to treat corneal blindness, by providing a clear optical media, in patients with an opaque cornea, who are not suitable candidates for Keratoplasty.

**Study Population:** 10 subjects suffering from unilateral or bi-lateral corneal blindness, not reasonably amenable by transplanting human tissue. The KPro can be implanted in OD or OS (selection is according to PI discretion).

Study Duration: Subjects will be followed up for 12 months following device implantation

**Inclusion criteria** – (i) Male or female aged  $\geq 18$  and  $\leq 80$  years on the day of screening; (ii) Candidates must have the ability and willingness to attend all scheduled visits and comply with all study procedures; (iii) keratoprosthesis surgery is indicated in cases when keratoplasty is not a reasonable option or following a verifiable history of prior failed corneal transplantation. (iv)Indications that fall under poor candidate for keratoplasty include but are not limited to: herpetic keratitis, vascularized corneal scar, Ocular Cicatricial Pemphigoid, alkali burn, Steven Johnson Syndrome, and limbal stem cell deficiency; (v) pseudophakia; (vi) adequate tear film and lid function; (vii) perception of light in all quadrants; (viii) Female patients of childbearing age must have negative pregnancy test at screening and agree to use an effective method of contraception throughout the study.

**Exclusion criteria** – (i) reasonable chance of success with traditional keratoplasty; (ii) current retinal detachment; (iii) connective tissue diseases; (iv) end stage glaucoma; (v) history or evidence of severe inflammatory eye diseases (i.e. uveitis, retinitis, scleritis) in one or both eyes within 6 months prior to planned implantation; (vi) history of ocular or periocular malignancy; (vii) history of extensive keloid formation; (viii) any known intolerance or hypersensitivity to topical anaesthetics, mydriatics, or component of the device; (ix) signs of current infection, including fever and current treatment with antibiotics; (x) severe generalized disease that results in a life expectancy shorter than a year; (xi) any clinical evidence that the investigator feels would place

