# 5.2 Endpoints

# 5.2.1 Primary Safety Endpoint

The frequency and severity of all unanticipated adverse device-related events (UADE) or treatment-related adverse events, during and after implantation of the CorNeat KPro device up to 12 months should be less than SOC (as detailed in section Known Potential Risks).

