# 5.2.2 Effectiveness Endpoints:

Primary Effectiveness Endpoint: Device retention Secondary Effectiveness Endpoint: Improvement in visual acuity

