### 10.8 Known Potential Risks

Known risks from usage of similar artificial corneas are:

- Postoperative Corneal Melt is one of the most severe complications that can occur after keratoprosthesis surgery with incidence of up to 30%. It may lead to scarring, irregular astigmatism, photophobia, decreased vision, and even endophthalmitis.
- Lack of graft retention Corneal grafts tissue artificial integration is limited and with time the bond between the implant and eye weakens. E.g. Boston KPro's retention rates decreases over time with incidence of lack of retention of 6, 11 and 25% after 1, 2- and 5-years post-op, respectively.
- Post-operative Glaucoma is the most important threat to long-term preservation of vision following Boston KPro surgery with elevation of intraocular pressure in 19–38 % of patients postoperatively and progression of pre-operative glaucoma in 7–14 % of patients. Development of glaucoma de novo following Kpro placement has been reported in 2-28% of KPro recipients .
- Poor post-operative visual quality Eyes with current KPros have very limited visual field and poor visual function. About 50% of patients implanted with Boston KPro maintain 20/200 CDVA after 8 years from surgery .

<sup>6 Bouhout, S., Robert, M.C., Deli, S. and Harissi-Dagher, M., 2018. Corneal melt after Boston keratoprosthesis: Clinical presentation, management, outcomes and risk factor analysis. Ocular immunology and inflammation, 26(5), pp.693-699.

<sup>7 Schaub, F., Bachmann, B.O., Seyeddain, O., Moussa, S., Reitsamer, H.A. and Cursiefen, C., 2017. Mid-and longterm experiences with the Boston-keratoprosthesis. The Cologne and Salzburg Perspective. Klinische Monatsblatter fur Augenheilkunde, 234(6), p.770.

<sup>8 Jin, B. and Zhu, X., 2017. The pathogenesis and prevention of corneal graft melting after keratoplasty. J Clin Ophthalmol, 1(1), p.10.

<sup>9 Ciolino, J.B., Belin, M.W., Todani, A., Al-Arfaj, K., Rudnisky, C.J. and Boston Keratoprosthesis Type 1 Study Group, 2013. Retention of the Boston keratoprosthesis type 1: multicenter study results. Ophthalmology, 120(6), pp.1195-1200.

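### The protocol gives two different objectives and three differently named primary endpoints, and its proof of efficacy rests on device retention with no time point or criterion

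*Protocol*

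**What the plan says.** - **Objective.** The synopsis (section 3, Objectives) states: "The objective of this clinical study is to prove the safety of the CorNeat Keratoprosthesis (KPro". Section 5.1 states: "The objective of this clinical trial is to prove the safety and efficacy of the CorNeat KPro device intra and post-operatively". The study title, in the synopsis and again in section 6, mentions both safety and efficacy.
- **Primary safety endpoint.** Under 5.2.1, and in the same terms in the synopsis, the frequency and severity of unanticipated device-related or treatment-related adverse events "up to 12 months should be less than SOC (as detailed in section Known Potential Risks".
- **Primary effectiveness endpoint.** Section 5.2.2 reads "Primary Effectiveness Endpoint: Device retention", and the synopsis reads "Primary Endpoint: Retention of implant". Neither adds a time point, a target rate or a comparator. Improvement in visual acuity is secondary in both places.
- **Section 6.** It labels ocular wall integrity at the implant site as primary and absence of conjunctival irritation as secondary. Neither appears in 5.2.
- **Known Potential Risks (10.8).** The list of risks of similar artificial corneas gives, as an example for the Boston KPro, "incidence of lack of retention of 6, 11 and 25% after 1, 2- and 5-years post-op, respectively".
- **Analysis.** The synopsis sets the sample of 10 on a non-statistical basis. Section 12.2.3 says that no separate SAP is in use because no statistical methods are applied. It then describes adverse-event listings, counts and percentages, and says nothing about retention.

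**The concern.** A reader cannot tell from the protocol what the trial is meant to establish or which endpoint carries it. Depending on the section consulted, the aim is safety, or safety and efficacy. The primary endpoint is adverse events, retention or ocular wall integrity.

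This matters most for efficacy. Section 5.1 promises proof, but the endpoint that would supply it has nothing attached that a result could fail. The study is open label and no later analysis document will close the gap, so what counts as adequate retention could be settled once the outcomes are known. Device loss also appears in the risk list to which the safety endpoint refers. The same loss could thus be weighed unfavourably under safety and presented favourably under effectiveness. The protocol does not say how the two relate.

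**Working it through.** **1. The texts side by side**

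| Place | Objective or primary label |
|---|---|
| Synopsis, Objectives | Prove safety |
| Section 5.1 | Prove safety and efficacy |
| 5.2.1 and synopsis | Primary: device- or treatment-related adverse events |
| 5.2.2 and synopsis | Primary: retention |
| Section 6 | Primary: ocular wall integrity |

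All of this is current text, not revision history. No section says which objective governs, whether both 5.2 primaries are needed, or how section 6 fits with them.

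**2. What a retention result could show**

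The sample size has no alpha, power or effect size behind it, so there is no calculation to reproduce. The inputs are n = 10 (synopsis and 7.1) and the one-year loss reference of 6% (10.8). Losses are assumed independent between subjects.

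*One loss in ten.* Loss rate = 1/10 = 10%, which is above 6%. Retention = 9/10 = 90%.
- Exact 95% lower limit for loss: 1 − 0.975^(1/10) = 0.0025, or 0.3%.
- Exact 95% upper limit U solves (1 − U)^10 + 10U(1 − U)^9 = 0.025, giving U = 0.445.
- The interval is 0.3% to 44.5% for loss, or 55.5% to 99.7% for retention.

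The 10% and the 90% are one fact. Set beside the reference, it looks unfavourable. Under 5.2.2 there is nothing to set it against.

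*No losses in ten.*
- One-sided 95% upper limit: (1 − U)^10 = 0.05, so U = 1 − 0.05^(1/10) = 0.259.
- Two-sided 95% upper limit: 1 − 0.025^(1/10) = 0.308.

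The best possible result is therefore compatible with a loss rate about four times the reference (25.9/6 = 4.3).

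*Subjects needed for zero losses to put the one-sided 95% limit below 6%.* 1 − 0.05^(1/n) < 0.06 requires n > ln 0.05 / ln 0.94 = 48.4, so n = 49. Ten subjects cannot support a claim of proof against that figure, whatever is observed.

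**The case against.** The case on the other side has four parts.

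- **Layout.** A primary safety endpoint beside a primary effectiveness endpoint is an ordinary device-study layout. With no hypothesis tested, no error rate depends on how the two combine. This stands: two primaries are not in themselves a fault.
- **Descriptive study.** The trial is first-in-human and says that no statistics are needed. That would answer the point if the wording agreed, but both objectives speak of proof and the safety endpoint carries a comparison. If description is intended, the text should say so.
- **A 6% bar.** A reader might infer that the protocol sets a pass/fail limit of less than 6% on device loss inside the safety endpoint. The documents do not support that. Section 5.2.1 sets one comparison for the frequency and severity of all qualifying events ("should be less than SOC (as detailed in section Known Potential Risks"), not a rule for each listed risk. The 6% is an example from another keratoprosthesis, while 4.1.2 and 4.2.4 treat keratoplasty as the standard of care. A loss also enters the safety endpoint only if recorded as unanticipated and device-related, or as treatment-related. For the same reason, no probability of conflicting primary results can be derived. The chance of at least one loss in ten (46.1% if the true rate is 6%) is the chance of a loss, not of contradictory conclusions.
- **Safety as this trial's target.** A reader might also take the sample-size justification (synopsis and 12.2.2) as naming safety as the target of this trial. It describes the cited FDA guidance. Only the synopsis sample-size consideration speaks of this study as assessing safety.

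**Conclusion.** The point holds as an inconsistency that affects what the trial may conclude. The objective differs between the synopsis and 5.1. The primary label falls on three different things across 5.2 and section 6. Efficacy is to be proven on an endpoint without a time point or criterion. As written, any retention figure could be reported as success, including 90%, although a 10% loss is above the only one-year reference the protocol cites. The data could not prove efficacy in any case: zero losses in ten still leaves an upper limit of about 26%.

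The limits assume independent losses and complete 12-month data on ten subjects. The comparison with 6% is for context only, since the protocol does not make that figure a formal criterion. The three-patient stopping rule in 10.11 concerns halting the trial and supplies no success criterion for retention. The correction should be made, but it does not call for a redesign.

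**What to change.** 1. State one objective in both the synopsis and 5.1: to assess safety, with effectiveness described and not proven.
2. Reconcile the primary and secondary labels in section 6 with those in 5.2.
3. In 5.2.2 and the synopsis, define retention as the device in place at month 12, counting every loss whatever its relatedness. Report it descriptively, with an exact confidence interval, beside the 6% one-year reference (identified as coming from another keratoprosthesis). Make no separate success claim.
4. State that device losses judged treatment-related are also listed under the safety endpoint. Retention should not be derived from that safety count, because losses judged unrelated would then drop out and retention would be overstated.

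The cost is wording in the synopsis, 5.1, 5.2.2 and section 6, with a line in 12.2.3 for the interval. No further subjects or visits are needed. The sponsor gives up a stand-alone effectiveness claim from this cohort, a small loss since ten subjects could not have supported one.
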